9.6.2 Treatment Period (Treatment Weeks 1-50)

Patients who enter the Treatment Period on Visit 1a will be in the Treatment Period for up to 50 weeks and thus are eligible to receive study drug for up to 50 weeks.

Patients entering the Treatment Period after being followed in the Observation Period will have a variable number of weeks on treatment depending on how many weeks they were in the Observation Period. The total amount of time spent in the combined two periods of the study (Observation and Treatment) cannot exceed 50 weeks. The maximum number of weeks that a patient entering the Treatment Period from the Observation Period will be on study drug (Treatment Period) is 46 weeks. Patients enter the Treatment Period from an Observation Visit (OV) when their Worst itch NRS is greater than or equal to 5 (≥ 5).

Regardless of how many treatment weeks the patient was on study drug, all patients who enter the Treatment Period will complete End of Treatment Visit TV14 (unless consent is withdrawn). Since all patients must titrate to their maintenance dose over the first four weeks of the Treatment Period, Visits 1a/Visits 1b (TV 1) and TV 2 over the first four weeks of the Treatment Period will be common to all patients in TR03ext regardless of when they enter into the Treatment Period. Patients who transition from the Observation

Period to the Treatment Period at a respective Observation Visit will follow the Treatment Visit schedule outlined in [Table 8](#).

9.6.2.1 Treatment Period Weeks 2-4 (Titration Phase of Study Drug)

The first week in the Titration phase is initiated as part of Visit 1a/1b (Day 1 Treatment Week 1, see [Section 9.6.1](#) and [Section 9.6.4](#)). Subsequently, the following events TC1, TV2 and TC2 will be conducted during the remainder of the titration phase. See [Table 5](#) for the Schedule of Events during the titration phase.

9.6.2.1.1 Telephone Contact Number 1 (TC1, Treatment Week 2)

The patient is to be contacted by phone and the following are to take place:

- record AEs
- reinforce and document patient's compliance with dosing and all other required study procedures (i.e. rescue medication log, dosing diary, etc.)
- confirm that patient has titrated drug in accordance with the dosing schedule on [Table 3](#)
- document tolerability/intolerability to study drug and decision to continue dose titration/maintenance following the dosing schedule of [Table 3](#)
- discontinue study medication in patients who do not tolerate 30 mg BID dose and complete the End of Treatment Visit, TV14 (See [Section 9.6.2.2.12](#) and [Section 11](#))

9.6.2.1.2 TV 2 (Treatment Week 3)

The following procedures are to take place at this visit:

- complete PAS
- obtain vital signs
- collect urine for pregnancy test (regardless of sexual activity and confirm negative status prior to dispensing additional study drug)
- collect blood for PK
- perform 12-Lead ECG after at least 5 minutes in a supine position (See the Study Reference Manual for ECG procedures, [Section 17.4](#) Electrocardiograms for the handling of Cardiovascular adverse events)
- perform brief neurological assessment
- administer PRO measurements (paper versions):
 - Worst itch NRS
 - Average itch intensity NRS
 - VRS
 - ItchyQoL
 - MOS Sleep-R
 - HADS.

The PRO questionnaires must be administered at the study site under the supervision of and by trained study staff, strictly adhering to PRO Administration Instructions (see Study Reference Manual).

- record AEs (including tolerability to study drug)
- review concomitant medications, including over-the-counter medications, nutritional supplements, and vitamins
- reinforce and document patient's compliance with dosing and all other required study related procedures (i.e. rescue medication log, dosing diary, etc.)
- perform Study Drug accountability, retrieve previously dispensed Study Drug
- dispense enough Study Drug to the patient for required dosing until their return at TV3 (Treatment Week 5)
- document tolerability/intolerability to study drug and titration decision based on [Table 3](#)
- discontinue study medication in patients who do not tolerate 30 mg BID dose and complete the End of Treatment Visit, TV14 (See [Section 9.6.2.2.12](#) and [Section 11](#))

9.6.2.1.3 Telephone Contact Number 2 (TC2, Treatment Week 4)

The patient is to be contacted by phone and the following are to take place:

- record AEs
- reinforce and document patient's compliance with dosing and all other required study procedures (i.e. rescue medication log, dosing diary, etc.)
- instruct the patient on dose titration/maintenance based on [Table 3](#)
- patients reporting intolerable side effects at their current dose should titrate down to a tolerable preceding dose and this should be record as the patient's maintenance dose
- patients at any dose who reported intolerable AEs for the previous week (Week 3 on drug) and continue to report intolerable AEs on this visit, should be discontinued from study drug and scheduled for the End of Treatment Visit, TV14 (See [Section 9.6.2.2.12](#) and [Section 11](#))

9.6.2.2 Treatment Period Weeks 5-50

During this period of the study, the patient continues on the maintenance dose established by the end of Treatment Week 4 for the remainder of the study with the exception of two allowable dose reductions permitted during Treatment Weeks 5 – 50 (e.g., a patient at 90 mg BID can be reduced to 60 mg BID and then subsequently to 30 mg BID). If a third dose reduction is needed, the patient should be discontinued from the study (See [Table 3](#), [Section 9.6.2.2.12](#) and [Section 11](#)). Patients who are on the 30 mg BID dose will be discontinued if a dose reduction is required.

See [Table 6](#) for the Schedule of Events for Treatment Weeks 5-50.

9.6.2.2.1 TV 3 (Treatment Week 5)

The following procedures are to take place at this visit:

- complete PAS
- administer the Worst Itch NRS (paper version) and evaluate against the Failure-to-Improve criteria (see [Section 11.1](#))

For patients who MEET the Failure-to Improve criteria:

- Stop study medication
- Perform End of Treatment Visit (TV14) procedures

For patients who DO NOT meet Failure-to-Improve criteria, perform the following procedures:

- obtain vital signs
- collect urine for pregnancy test (regardless of sexual activity) and confirm negative status prior to dispensing additional study drug
- collect blood for PK
- perform 12-Lead ECG after at least 5 minutes in a supine position (See the Study Reference Manual for ECG procedures, [Section 17.4](#) Electrocardiograms for the handling of Cardiovascular adverse events)
- perform brief neurological assessment
- administer PRO measurements (paper versions):
 - Average itch intensity NRS
 - VRS
 - ItchyQoL
 - MOS Sleep-R
 - HADS

The PRO questionnaires must be administered at the study site under the supervision of and by trained study staff, strictly adhering to PRO Administration Instructions (see Study Reference Manual).

- record AEs
- review of concomitant medications, including over-the-counter medications, nutritional supplements, and vitamins
- reinforce and record patient's compliance with dosing and all other required study procedures (i.e. rescue medication log, dosing diary, etc.)
- perform study drug accountability, retrieve previously dispensed study drug
- dispense enough study drug to the patient for required dosing until their next Treatment Visit

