Patients with a Worst Itch NRS greater than 5 (≥ 5) enter the Treatment Period and will receive Study Drug starting with an evening 30 mg dose (to be taken at home), after the Visit 1a (or Visit 1b) procedures have been completed.

Receipt of the first dose of study drug will define Day 1. Visit 1a or Visit 1b for these patients is also Treatment Visit 1 (TV1). Subsequent visits will be defined as TV2, TV3, etc.

Patients with a Worst Itch NRS less than 5 (<5) enter the Observation Period and will not receive study drug treatment. Visit 1a for these patients is also Observational Visit 1 (OV1). Subsequent visits will be defined as OV2, OV3, etc.

Patients in the observation period can be followed for up to 12 weeks.

If during the Observation Period, a patient's Worst Itch NRS increases to greater than or equal to 5 (≥ 5) and the patient meets all other eligibility criteria, Visit 1b procedures are to be performed. The patient's next visit will be Treatment Visit 2 (TV2). Do not repeat the Worst Itch NRS during Visit 1b.

If, however, at Observation Visit 12 the patient does not have a Worst Itch NRS greater than or equal to 5 (≥ 5), the patient will be screen failed without having initiated treatment with nalbuphine.

[Figure 2](#), [Figure 3](#) and [Figure 4](#) visually display the relationship between TR03ext study weeks, Treatment Period weeks and Observation Period weeks.

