9.6.2.2.12 TV 14 (End of Treatment Visit)

This visit applies to all patients who completed TV13; including patients who met Failure-to-Improve criteria at any Treatment Visit during the study (unless consent is withdrawn).

For patients who DID NOT meet Failure-to-Improve criteria during the conduct of the study, this visit (TV14) takes place after the patient has completed dosing with study medication.

- For patients who entered the Treatment Period at Visit 1a, TV14 will take place during week 51; four (4) weeks after TV13, as these patients should complete 50 weeks of treatment prior to TV14
- For patients who entered the Treatment Period at Visit 1b see [Table 8](#) for information on when TV14 is to take place

The following procedures are to take place at this visit:

- complete PAS
- obtain vital signs
- perform physical examination
- perform brief neurological assessment
- complete the PAS

- perform 12-lead ECG after at least 5 minutes in a supine position (See the Study Reference Manual for ECG procedures, [Section 17.4](#) Electrocardiograms for the handling of Cardiovascular adverse events)
- collect blood for central laboratory (hematology and chemistry) and serum pregnancy test (regardless of sexual activity) for central laboratory
- collect urine for urinalysis at the central laboratory
- collect blood for PK
- perform skin biopsy (optional procedure at select sites only). Obtain 3 samples (i.e., H&E, nerve fiber density (histology) and MOR/KOR density (histology, Western Blot)); see the Lab and Study Reference Manuals for details
- administer PRO measurements (paper versions):
 - Worst itch NRS
 - Average itch intensity NRS
 - VRS
 - ItchyQoL
 - MOS Sleep-R
 - HADS
 - SOWS

The PRO questionnaires must be administered at the study site under the supervision of and by trained study staff, strictly adhering to PRO Administration Instructions (see Study Reference Manual).

- record AEs
- review of concomitant medications, including over-the-counter medications, nutritional supplements, and vitamins
- perform study drug accountability, final retrieval of any previously dispensed study drug
- retrieve the Dosing Diary
- Dispense the 14 Day SOWS packet, instruct the patient on how to complete the scales and to complete the scales daily for 14 days
- Schedule the patient for the Washout and Safety Follow-up Period Visit

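### At TV3–TV13 the stop rule is scored before the other questionnaires are given, and stopped patients then repeat the Worst Itch NRS, so their end-of-treatment scores can be given knowing the drug has been withdrawn

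*Protocol*

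**What the plan says.** Section 9.6.2.2.1 (TV3) opens with "The following procedures are to take place at this visit". The first item is the PAS. The second is to "administer the Worst Itch NRS (paper version) and evaluate against the Failure-to-Improve criteria". The text then divides:

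- Patients who meet the rule stop the drug. The next item is "Perform End of Treatment Visit (TV14) procedures".
- The other branch begins "For patients who DO NOT meet Failure-to-Improve criteria, perform the following procedures". Its list contains Average itch NRS, VRS, ItchyQoL, MOS Sleep-R and HADS.

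Sections 9.6.2.2.2 to 9.6.2.2.11 (TV4 to TV13) have the same structure, with trivial differences in wording.

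Section 9.6.2.2.12 says that TV14 applies to everyone who completed TV13, "including patients who met Failure-to-Improve criteria at any Treatment Visit during the study (unless consent is withdrawn". Its questionnaire list starts with "Worst itch NRS" and continues with the same five questionnaires and the SOWS. The PAS is listed as well. Footnote 17 of Table 6 also sends patients who meet the rule to the TV14 procedures. Neither place exempts a form already completed that day.

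Where an itch score moves a patient from observation to treatment, Section 9.6 does have such a rule: "Do not repeat the Worst Itch NRS during Visit 1b".

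**The concern.** The Worst Itch NRS that triggers the stop is taken before the decision. Everything else the patient reports at that visit comes after it, including a second Worst Itch NRS for those who are stopped. The study is open label (Section 10.3), and drug is withdrawn because of the patient's own answer. Mood, quality of life and itch are subjective, and a patient who has just learned this may answer differently.

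Two secondary objectives in Section 4.2 use these scores: change from baseline to the final Treatment Period Visit, and change in the questionnaires during washout, for which TV14 is the starting point. For a stopped patient both rest on forms that follow the stop.

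The duplicate reading is a separate difficulty. A patient can be recorded as a failure on one Worst Itch value and as improved on another, both with 24-hour recall and both from one visit.

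**Working it through.** No arithmetic applies beyond a count and one worked case. The protocol gives no sample-size calculation and plans no tests, so there is no stated figure to reproduce. The check is of the order of procedures.

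1. **How many visits.** TV3 to TV13 is 13 − 3 + 1 = 11 visits. All eleven score the rule before the branch. A given patient can meet the rule only once, so the stopped-patient problem arises at one visit per patient.

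2. **Is the order binding?** Yes, as written. The five other questionnaires sit only inside branches that depend on the decision. This is more than the sequence of bullets in a list.

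3. **Is TV14 done at the same visit?** This is inferred, on four grounds:
   - Both branches stand under the lead-in "The following procedures are to take place at this visit".
   - Section 9.6.6 dates the end of drug to the visit at which the rule was met.
   - Section 9.6.2.2.12 sets a later TV14 date only for patients who did not meet the rule.
   - Section 9.6.2.1.3 speaks of scheduling patients for TV14, whereas TV3 to TV13 say to perform its procedures.

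   Section 11.1 taken alone would allow another day. The TV14 scores would still follow the stop.

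4. **Can the two Worst Itch values disagree in a way that matters?** The examples in Section 11.1 use a baseline of 5: a score of 5 stops treatment and a score of 4 does not. If the first reading is 5 and the TV14 reading is 4, the patient is a failure by rule (5 ≥ 5) and shows a change of 4 − 5 = −1 at end of treatment.

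5. **Which value would count?** By visit label, the Treatment Visit reading decides failure and the TV14 reading is the end-of-treatment score. Section 9.6.2 has all treated patients complete TV14, and Section 9.6.3 names it as the final Treatment Period visit for patients entering from observation. On that reading, the value that enters the change from baseline is the one taken after the stop.

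6. **What is not affected.** Failure status uses the first reading, so its frequency and timing stand. The first PAS of the visit also precedes the decision.

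**The case against.** The strongest reply is that patient knowledge is inferred. The protocol does not say when the patient is told, and staff could score the rule, say nothing and hand over the remaining forms. The questionnaire instructions in the Study Reference Manual, which is not at hand, might set an order. This stands as a limit. Even so, the protocol lists the stop before the TV14 procedures and nothing in it withholds the result, so the exposure is permitted even if it does not always occur.

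Several forms also look back beyond the moment: four weeks for MOS Sleep-R, one week for ItchyQoL and HADS, 24 hours for both NRS. Only the VRS asks about today. That may dampen an effect but does not exclude one.

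The Visit 1b comparison should not be pressed too far. The protocol gives no reason for forbidding the repeat, and at Visits 1a and 1b the other questionnaires also come after the itch score has decided entry. What it shows is that a no-repeat rule was available and was not used here.

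The stakes are moderate. The primary endpoint is treatment-emergent adverse events (Section 5.1), and efficacy is summarized without testing (Section 19.8.1). Patients who complete treatment also answer TV14 after dosing has ended, though not because of their own score. A choice between two same-day values can be left to the SAP. The SAP cannot, however, undo answers already given after the decision.

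A reader might infer three stronger claims that the protocol does not support:

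- That patients always know the result when they complete the forms. Disclosure is not timed.
- That continuing patients score better because they received good news. Continuing is the status quo for them, and such an effect is speculative.
- That the final-visit mean shifts by a particular amount. The shift would be the share of final visits that are failure visits times the effect of the news. Assuming a share of 20–50% and an effect of 0.5–1 point gives 0.2 × 0.5 = 0.10 to 0.5 × 1 = 0.50 points, but neither input is in the protocol, and the direction is unknown.

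**Conclusion.** The point holds for patients stopped under the failure-to-improve rule. Their end-of-treatment questionnaires are placed after the stop, in an open-label study, and feed two secondary objectives. The Worst Itch NRS and the PAS are listed twice for what appears to be one visit.

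This rests on two inferences: that TV14 is done at the qualifying visit, and that the patient may know the result by then. If TV14 falls on a later day, the duplicate is no longer within one visit, but the scores still follow the stop.

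The protocol permits the exposure; it does not demonstrate a bias, and neither size nor direction can be derived. The change is worth making because it costs almost nothing.

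**What to change.** In Sections 9.6.2.2.1 to 9.6.2.2.11, have the patient complete the Worst Itch NRS, Average itch NRS, VRS, ItchyQoL, MOS Sleep-R and HADS together, before staff score the failure-to-improve rule or disclose its result. Then branch.

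For patients who meet the rule, state in Section 9.6.2.2.12 and in footnote 17 of Table 6 that these six forms and the PAS already done at that visit serve as the TV14 values and are not repeated. Add only the items specific to TV14. The SOWS and the PBI-P (assigned to TV14 in Table 6) would still follow the decision, since continuing patients do not complete them.

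The cost is a reordering of visit text. Both branches already require the five other questionnaires, so continuing patients have no added burden, and stopped patients complete one Worst Itch NRS and one PAS fewer. The stopping rule itself is untouched.

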9.6.2.2.2 TV 4 (Treatment Week 9)

The following procedures are to take place at this visit:

- complete PAS

- administer the Worst Itch NRS (paper version) and evaluate against the Failure-to-Improve criteria (see [Section 11.1](#))

For patients who MEET the Failure-to Improve criteria:

- Stop study medication
- Perform End of Treatment Visit (TV14) procedures

For patients who DO NOT meet Failure-to-Improve perform the following procedures:

- obtain vital signs
- collect urine for pregnancy test (regardless of sexual activity) and confirm negative status prior to dispensing additional study drug
- collect blood for PK
- perform 12-Lead ECG after at least 5 minutes in a supine position (See the Study Reference Manual for ECG procedures, [Section 17.4](#) Electrocardiograms for the handling of Cardiovascular adverse events)
- perform brief neurological assessment
- administer PRO measurements (paper versions):
 - Average itch intensity NRS
 - VRS
 - ItchyQoL
 - MOS Sleep-R
 - HADS

The PRO questionnaires must be administered at the study site under the supervision of and by trained study staff, strictly adhering to PRO Administration Instructions (see Study Reference Manual).

- record AEs
- review of concomitant medications, including over-the-counter medications, nutritional supplements, and vitamins
- reinforce and document patient's compliance with dosing and all other required study procedures (i.e. rescue medication log, dosing diary, etc.)
- perform study drug accountability, retrieve previously dispensed Study Drug
- dispense enough study drug for required dosing until the patient returns for their next Treatment Visit

9.6.2.2.3 TV 5 (Treatment Week 13)

The following procedures are to take place at this visit:

- complete PAS
- administer the Worst Itch NRS (paper version) and evaluate against the Failure-to-Improve criteria (see [Section 11.1](#))

For patients who MEET the Failure-to Improve criteria:

- Stop study medication

- Perform End of Treatment Visit (TV14) procedures

For patients who DO NOT meet Failure-to-Improve perform the following procedures:

- obtain vital signs
- collect urine for pregnancy test (regardless of sexual activity) and confirm negative status prior to dispensing additional study drug
- collect blood for PK
- perform 12-Lead ECG after at least 5 minutes in a supine position (See the Study Reference Manual for ECG procedures, [Section 17.4](#) Electrocardiograms for the handling of Cardiovascular adverse events)
- perform brief neurological assessment
- administer PRO measurements:
 - Average itch intensity NRS
 - VRS
 - ItchyQoL
 - MOS Sleep-R
 - HADS

The PRO questionnaires must be administered at the study site under the supervision of and by trained study staff, strictly adhering to PRO Administration Instructions (see Study Reference Manual).

- record AEs
- review of concomitant medications, including over-the-counter medications, nutritional supplements, and vitamins
- reinforce and document patient's compliance with dosing and all other required study procedures (i.e. rescue medication log, dosing diary, etc.)
- perform study drug accountability, retrieve previously dispensed study drug
- dispense enough study drug to the patient for required dosing until their next Treatment Visit

9.6.2.2.4 TV 6 (Treatment Week 17)

The following procedures are to take place at this visit:

- complete PAS
- administer the Worst Itch NRS (paper version) and evaluate against the Failure-to-Improve criteria (see [Section 11.1](#))

For patients who MEET the Failure-to Improve criteria:

- Stop study medication
- Perform End of Treatment Visit (TV14) procedures

For patients who DO NOT meet Failure-to-Improve perform the following procedures:

- obtain vital signs
- collect urine for pregnancy test (regardless of sexual activity) and confirm negative status prior to dispensing additional study drug)
- collect blood for PK
- perform 12-Lead ECG after at least 5 minutes in a supine position (See the Study Reference Manual for ECG procedures, [Section 17.4](#) Electrocardiograms for the handling of Cardiovascular adverse events)
- perform brief neurological assessment
- administer PRO measurements (paper versions):
 - Average itch intensity NRS
 - VRS
 - ItchyQoL
 - MOS Sleep-R
 - HADS

The PRO questionnaires must be administered at the study site under the supervision of and by trained study staff, strictly adhering to PRO Administration Instructions (see Study Reference Manual).

- record AEs
- review of concomitant medications, including over-the-counter medications, nutritional supplements, and vitamins
- reinforce and document patient's compliance with dosing and all other required study procedures (i.e. rescue medication log, dosing diary, etc.)
- perform study drug accountability, retrieve previously dispensed study drug
- dispense enough study drug to the patient for required dosing until their next Treatment Visit

